PROTOCOL TITLE: *Use of simulation to improve ventricular assist device self-management: A Quantitative Study*

PRINCIPAL INVESTIGATOR:

*[name]
Department of Hospital Medicine and Medical Education
[contact]
[contact]*

VERSION NUMBER:

2

VERSION DATE:

7/3/17

OBJECTIVES:

AIM 1. Compare performance of VAD self-management skill of sterile dressing changes and VAD-related controller functions, between SBML-trained and the usual VAD training group immediately following training, and at one and three months after VAD implantation.

Hypothesis 1a: VAD patients and their caregivers will demonstrate better VAD self-management skills when trained with the SBML intervention compared to the usual VAD training group.

Hypothesis 1b: VAD patients and their caregivers will demonstrate better VAD self-management skill retention at one and three months compared to the usual VAD training group.

AIM 2. This exploratory aim will examine VAD-patient driveline infections, and all-cause and infection-related re-hospitalizations through one and three months after VAD implant, between the SBML intervention group as compared to the usual VAD training group.

Hypothesis: Patients who complete the SBML VAD curriculum with their caregivers will have lower infections and re-hospitalizations compared to the usual VAD training group.

BACKGROUND:

Over 5.1 million Americans suffer from heart failure (HF), with over \$32 billion expended annually.¹ Although survival from HF has improved, a diagnosis of HF is similar to some forms of cancer, with 50% of patients dying within 5 years of diagnosis.¹ Ventricular assist devices (VADs) have improved survival in patients with advanced HF.² Over 17,000 patients with advanced HF have received VADs in the last decade, and implantation rates are expected to increase with newer generation devices.³ VADs may be used as “destination” (e.g., permanent) therapy or as a “bridge to transplant.” Patients on Destination Therapy will remain on the VAD for the rest of their lives. Bridge to Transplant patients will remain on the VAD until time of heart transplant. VAD devices are surgically implanted into the apex of the left ventricle of the heart and are connected to the aorta, providing circulatory support to the patient. A driveline passes from the device through the skin, connecting to a system controller that in turn is connected to external power. A frequent and often deadly complication after VAD implantation is driveline infection. Infection can cause pump failure from thrombosis, which requires surgical pump exchange if the patient survives the event.⁴

Immediately prior, and around the time of VAD implantation, patients and their caregivers are educated about VAD self-management. However, patients are often critically ill during this hospitalization, and caregivers (often family) are under emotional duress; thus skill retention with this traditional education may be lacking. After discharge, patients and caregivers are required to engage in significant daily VAD self-management including: driveline exit site dressing changes; performing controller self-tests; changing power sources; troubleshooting emergent VAD-related malfunction; and recognizing VAD-specific signs and symptoms requiring immediate contact with the VAD team. With insufficient VAD-related knowledge and improper VAD self-management, these patients can die from **preventable** complications including driveline infections.⁵

Unfortunately, no rigorous standardized training exists for patients and caregivers to ensure mastery of VAD self-management. Traditionally, VAD training occurs via the "see one, do one, teach one" method, where a VAD patient and caregiver watches a video or live demonstration of VAD-related techniques (e.g., dressing changes), and are then expected to perform the task, first under supervision, and, within days, independently. This process leads to uneven skill acquisition and may cause unnecessary harm to the patient. Simulation-based mastery learning (SBML) can be used to prevent such uneven skill acquisition and potential patient harm.⁶⁻¹⁴ Mastery learning is an intense form of competency-based education in which learners are required to meet or exceed a predetermined level of skill.¹⁵⁻¹⁷ In mastery learning, training *time* varies, but *outcomes* (skill achievement) are uniform. Current technology allows for SBML, in which learners must demonstrate mastery in a simulated setting before performing the skill in actual clinical practice. Our research demonstrates that SBML is a more effective strategy than traditional education in improving various clinical skills and patient care for procedures such as Advanced Cardiac Life Support,^{14,18,19} paracentesis,^{8,11} lumbar puncture,⁶ and central venous catheter insertion^{7,10,12,13} and maintenance.⁹ Proper techniques for central line maintenance are similar to driveline care. Therefore, we propose to create and test an SBML intervention for VAD self-management skills and compare the intervention to traditional (usual) VAD training.

LITERATURE CITED

Each individual enrolled will participate in the study for approximately 3 months. We anticipate enrollment of study subjects will take approximately 15 months. We hope to complete all analyses 2 two years.

STUDY ENDPOINTS:

The primary study endpoints are we have enough patients enrolled to compare VAD-care SBML training and usual training groups.

PROCEDURES INVOLVED:

Approximately 60 advanced HF patients undergo VAD implantation at NMH yearly. During our 15-month study period, up to 75 participating patients and 75 caregivers will be eligible to receive either the SBML VAD self-management curriculum or usual VAD training. Eligible patients will be about to undergo VAD implantation at NMH, age >18, and English-speaking. Eligible caregivers will be identified by a VAD implantation patient, age >18, and English-speaking. Advanced HF patients who are scheduled for VAD implantation will receive information about the study at their pre-implantation clinic visits or during hospitalization. Consenting patients will be asked to provide the name and contact information of their primary caregiver; we will contact the caregivers to explain the study and assess their interest. Patients and caregivers must both agree to participate in the study to be enrolled. All Patient and caregiver VAD self-management training begins before implantation and continues up to the hospitalization for VAD placement.

Study randomization will be conducted via random number generator. After randomization, demographic data including age, sex, race/ethnicity, and socioeconomic (SES) factors such as zip code, highest level of education, and employment status will be collected from patients and caregivers.

Two VAD nurses will perform usual training only, which is the current standard of care. First, patients and caregivers watch a video produced by the VAD manufacturer. Subsequently, the VAD nurse trains the patient and caregiver per usual routine with a non-implanted VAD. These meetings occur 1 to 3 times depending upon patient and caregiver availability and are not standardized. During the VAD implantation hospitalization, the caregiver completes a written examination to assess knowledge. The VAD nurse observes patient and caregiver completion of skills and deems competence based only on observation. Historically, patient and caregivers are variably able to participate in training sessions. If the patient is too ill to participate in training before VAD implantation, only the caregiver completes training and the patient is trained during the hospital stay for implantation at which point they are significantly clinically improved.

Three VAD nurses will administer SBML training. The SBML training group will first 1) watch the VAD video, then 2) participate in pre-intervention assessments using the simulator for a) driveline exit site sterile dressing changes; b) performing controller self-tests; c) changing power sources; d) troubleshooting emergent VAD-related malfunction; and e) recognizing specific signs and symptoms requiring immediate contact with the VAD team. The patient and caregiver

then will participate in deliberate practice on the simulator with feedback from the instructor. We anticipate 2 training sessions of 1-2 hours each to become proficient in these skills. After training, the patient and caregiver complete a post-intervention assessment on the simulator using the checklists. At the end of training, the patient and caregiver will complete the written examination to assess knowledge and will be required to meet or exceed the MPS on the checklists and written examination. If they fail to meet the MPS, they will receive additional training until they meet the MPS. If the patient is ever too ill, only the caregiver will participate in the training and the patient will be trained during the hospital stay for implantation. Both training groups. After training, we will ask participants to rate their educational experience and their confidence in performing each of the 5 VAD self-management tasks [via a questionnaire adapted from our previous work. All participants will demonstrate the five skill domains on the actual VAD patient during the implantation hospitalization (Time 0), and at one and three months after training to assess skill retention. Assessments will be performed during office visits, as patients are seen at least monthly after VAD implantation, or re-hospitalizations. If caregivers cannot attend, assessments will be performed via internet video. We anticipate the majority of enrolled patients will have internet access; alternatively, we will arrange sessions at their local library.

A trained VAD nurse (who is not assigned to teach the curriculum) will perform all patient and caregiver assessments using the checklist. In the absence of this nurse, the PI or a Co-I will perform assessments; we expect this to be rare. The trained VAD nurse, the PI and COCo-I will be blind to the intervention received by the patient and caregiver. A random sample of 25% of all assessments will be double scored by both the VAD nurse and PI or Co-I to assess inter-rater reliability.

After VAD implant, patients are managed by the VAD team with frequent office visits. Complications and re-hospitalizations are documented in outpatient and/or inpatient medical records. Patients admitted to a local hospital are typically transferred to NMH for care. If patient is admitted to another hospital, they are customarily transferred to NMH to manage the VAD. We believe we will be able to capture all data about driveline infections and re-hospitalizations prospectively.

NMH's infection prevention department also tracks *all* VAD related driveline infections using definitions in the INTERMACS database.³⁷ We will assess patient factors at time of infection and during re-hospitalization to evaluate differences between the SBML and usual VAD training groups such as age, sex, body mass index, and the Charlson comorbidity codes. The Charlson score is based on 19 chronic disease comorbidities derived from the International Classification of Disease Revision 9 (ICD-9) codes and predicts one-year mortality for hospitalized patients. We can obtain all admission ICD-9 codes from our Enterprise Data Warehouse⁹³ which also convert ICD-10 codes to their corresponding ICD-9. We will obtain additional data using the INTERMACS database (includes all NMH patients), which provides type of VAD, VAD indication (DT vs. BTT), and infection and re-hospitalization rates.

DATA AND SPECIMEN MANAGEMENT:

Primary outcome measures are comparisons of VAD-care checklist assessments on the patient and written examination scores between SBML and usual training groups. Secondary outcome measures include self-management skill decay in the five domains from 0 to 3 months and comparisons of post-training questionnaires between groups.

We will estimate checklist score inter-rater reliability using the Kappa (κ) coefficient^{84,87}. Our prior work shows the difference between traditional training and SBML interventions is approximately 33%; traditionally trained simulated skill checklist performance averages 61.47% (SD=24.48) items correct while SBML training performance averages 94.88% (SD=6.63).^{9,48,51,53,88} We anticipate the usual training group in our study will perform similarly to the traditionally trained healthcare providers in our prior studies. Sample sizes of 65 in each group (total =130) achieve 82% power to detect at least 10% difference between the usual group and the SBML training group assuming a mean checklist score of 85% in usual group (SD=25) and 95% in the SBML training group (SD=10) with a significance level of 0.05 using a two-sided t-test. As the distribution of % items correct is likely to be non-parametric, adding 15% requires 75 in each group.⁸⁹ Therefore, our study will be overpowered to detect a 33% difference. We will compare checklist scores on actual patient assessments between usual care and SBML-trained groups using the independent t-test or Wilcoxon rank sum test (if data are non-parametric). We will compare age, sex, race/ethnicity, level of education, employment status, zip code, type of VAD, and VAD indication (DT vs. BTT) between groups using either Chi Square test or independent t-tests. If there is a difference between the randomized groups in any of these variables at the level of $p \leq 0.1$, we will use multiple linear regression or multiple quantile regression (for non-parametric data) to assess these variables independently on scores between the two groups. We will measure skills decay between groups using an analysis of variance (ANOVA) or a non-parametric analysis of variance at 0, 1 and 3-month assessments. Questionnaire results will be compared between groups using Chi-Square, independent t-test, or Wilcoxon rank sum where appropriate.

We will compare driveline infections and re-hospitalization rates at one and three months after VAD implantation between the SBML and the usual training groups using the Chi Square test, recognizing that we may be underpowered for this exploratory aim due to the short study time frame. We will compare age, sex, race/ethnicity, level of education, employment status, zip code, type of VAD, VAD indication (DT vs. BTT), and Charlson scores between groups using either the Chi Square test or independent t-tests. If there is a difference between the randomized groups in any of these variables at the level of $p \leq 0.1$, we will perform multiple logistic regression to control for these independent variables between groups. If some patients have more than infection, we will use random effects modeling to account for clustering by patient.

The study PIs, co-investigators, as needed, VAD nurse, and Research Coordinator (RC) will have access to individually identifiable data. Otherwise, a unique identification code will be assigned to each enrolled patient, and all of the data entered into the system for that patient will be identified by this code rather than by name.

Socio-demographic and medical records data will be collected by INTERMACS and exported to a secure web server at Northwestern University. Socio-demographic data collected from VAD caregivers and checklist of VAD self-maintenance tasks-performance data will be collected on paper but will be de-identified using a unique identifier for each patient or caregiver. This data will be stored on a Northwestern Server that is password protected and encrypted. All data will be collected specifically for research purposes.

WITHDRAWAL OF PARTICIPANTS:

Participants are free to withdraw from the study at anytime without consequences.

RISKS TO PARTICIPANTS:

There are two potential risks of participating in this study for patients:

1. Potential for breach of patient confidentiality. This is a very serious potential risk to patients, but safety measures, as described above, have been put into place and are monitored by the Northwestern University IRB.

2. The simulation training may be superior or inferior to usual care, which means patients assigned to either simulation or usual care groups may receive worse VAD related self-management care training. We will review data from our study every 3 months and if there are significant differences in complications between groups, we will either stop the study or provide a cross-over arm.

POTENTIAL BENEFITS TO PARTICIPANTS:

There may be no potential benefit to the individuals participating in this study if the intervention proves equipose with the usual care. However, the information gained from these results will inform healthcare providers how to better train patients and their caregivers in self-management techniques. Furthermore, if the intervention is successful, the benefit to patients and their caregivers could be improved knowledge of VAD self-management techniques and reduction in VAD-related complications.

SETTING:

Patients will be recruited either at the medical center (while the patient is hospitalized) or during a clinic visit. Training and assessments will take place in the patient room or in NMH conference rooms.

RESOURCES AVAILABLE:

[name], MS, Principal Investigator

[name] is a Clinical Associate Professor in the Department of Medicine and Medical Education at Northwestern University Feinberg School of Medicine. He also serves as the Director of Simulation and Patient Safety and Associate Program Director for the Internal Medicine Residency Program. He has extensive experience with the use of simulation for healthcare education. He has lectured at national and international conferences on curricula development and procedure skills training, and has assisted several institutions in setting up simulation-based training programs similar to those described in this grant application. Additionally, [name] has close to 50 peer-reviewed publications using simulation-based mastery learning for training physicians and has won international awards for his research which has been previously funded by Agency for Healthcare Research and Quality. As PI of this study, [name] will be responsible for study design and IRB approval, administrative oversight and training of research personnel, curriculum development, simulation training, data acquisition storage and analysis, and manuscript preparation.

[name], Co-Investigator

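### The endpoint section makes enrolment the primary endpoint, while the data section names two primary measures with no rule for success, no explicit time point and no unit of analysis

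*Combined protocol and SAP*

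**What the plan says.** - **STUDY ENDPOINTS:** "The primary study endpoints are we have enough patients enrolled to compare VAD-care SBML training and usual training groups". The section names no other primary endpoint.
- **DATA AND SPECIMEN MANAGEMENT, outcomes:** "Primary outcome measures are comparisons of VAD-care checklist assessments on the patient and written examination scores between SBML and usual training groups". The next sentence reads: "Secondary outcome measures include self-management skill decay in the five domains from 0 to 3 months", and it adds the post-training questionnaires.
- **DATA AND SPECIMEN MANAGEMENT, sample size:** 65 per group (130 in total) for 82% power on a mean checklist score of 85% (SD 25) against 95% (SD 10), "with a significance level of 0.05 using a two-sided t-test". This is raised by 15% to 75 per group. The checklist comparison has a named test (t-test or Wilcoxon). The written examination has no named test, significance level or sample size.
- **PROCEDURES INVOLVED, skills:** "All participants will demonstrate the five skill domains on the actual VAD patient during the implantation hospitalization (Time 0", with repeats at one and three months. A nurse who does not teach the curriculum "will perform all patient and caregiver assessments using the checklist".
- **PROCEDURES INVOLVED, examination:** under usual training only the caregiver is described as taking the written examination. Under SBML both patient and caregiver take it.
- **OBJECTIVES, Aim 1:** skills are compared just after training (Hypothesis 1a), with retention at one and three months (Hypothesis 1b).
- **NUMBER OF LOCAL PARTICIPANTS:** 75 patients and 75 caregivers, one caregiver per patient.

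**The concern.** The section that should fix the trial's main claim contains no outcome. The section that does name outcomes names two and leaves three things open:

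- **Success rule.** It is not said whether the trial succeeds on either measure or only on both.
- **Time point.** No visit is attached to the primary measures. Aim 1 has three occasions. It counts the later two from implantation, whereas PROCEDURES INVOLVED counts them from training.
- **Unit of analysis.** Patients and caregivers are both scored, and the plan does not say whether the test uses patients, caregivers, pairs or everyone pooled.

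The type I error of the main claim therefore depends on a rule that is not written down. The power depends on a unit of analysis that is not written down either, and a choice made after the data are seen could not be told apart from one made in advance.

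**Working it through.** **1. The plan's own power figure.** Inputs from the sample-size paragraph: difference 10 points, SDs 25 and 10, 65 per group, two-sided 0.05.

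- Common SD = √[(25² + 10²)/2] = √362.5 = 19.04.
- Standard error = 19.04 × √(2/65) = 3.340, and 10/3.340 = 2.994.
- Power = Φ(2.994 − 1.960) = 84.9%. The exact pooled t gives 84.4% and Welch 84.1%.

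The stated 82% is slightly lower, so it errs on the cautious side; the gap is not part of this point. A Wilcoxon efficiency of 0.955 gives 83.3%. The inflation reproduces: 65 × 1.15 = 74.75, so 75.

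**2. Error rate for the two named measures.** Assume each is tested at 0.05; the plan states this level only for the checklist.

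- Either suffices, independent tests: 1 − 0.95² = 9.75%.
- Either suffices, correlated tests (simulated normal statistics, 400,000 draws): 9.4% at correlation 0.3, 9.0% at 0.5, 7.8% at 0.8. The documents give no correlation, so this is a range.
- Both must succeed: at most 5%, with no inflation. Joint power then cannot exceed the checklist power, and it cannot be computed because the plan gives no assumptions for the examination.

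**3. Cost of splitting alpha.** The two-sided critical value at 0.025 is 2.241.

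- 65 per group: Φ(2.994 − 2.241) = 77.4% (exact t 76.5%).
- 75 per group: standard error = 19.04 × √(2/75) = 3.109, 10/3.109 = 3.216, and Φ(3.216 − 2.241) = 83.5% (exact t 82.8%).
- About 73 per group are needed for 82%.

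These figures treat all participants as independent.

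**4. Effect of the unit of analysis.** The 75 per group is 150 in total, which equals 75 patients plus 75 caregivers, so the calculation implies pooling. With one role and equal allocation, each arm has 75/2 = 37.5, that is 37-38.

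- Standard error = 19.04 × √(2/37.5) = 4.397, and 10/4.397 = 2.274.
- Power = Φ(2.274 − 1.960) = 62% (exact t 61-62%).

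If the roles are pooled and pairs share an arm, the effective size per arm is 75/(1 + ρ), where ρ is the within-pair correlation. The documents do not give ρ. At ρ = 0 the size is 75 and power is Φ(3.216 − 1.960) = 90%. At ρ = 1 it is 37.5 and power is 62%. The truth lies between.

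**The case against.** The best defence is that the intention can largely be pieced together. The data section labels its primary measures explicitly. Aim 1 separates initial skill from retention, and decay from 0 to 3 months is secondary, so Time 0 is the natural primary visit. The power calculation uses one mean checklist score in percent correct, which points to a total score. All of this stands, and it is why the fix follows that reading. But the reading has to be inferred, and it supplies neither a success rule nor a unit of analysis.

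The objection also disposes of several stronger claims that a reader might infer:

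- **That everything is tested at 0.05.** The level appears once, in the checklist sample-size sentence. For the examination it is an assumption.
- **That the primary comparison spans five domains and two roles.** Six tests would give 1 − 0.95⁶ = 26.5%, and twelve would give 1 − 0.95¹² = 46.0%. The plan sets out no such tests. The data section mentions the five domains only for the secondary decay outcome, and no separate role tests are planned. A count of twelve would also need an examination comparison in patients, for which no usual-training data are described.
- **That Aim 1 covers only two of the five skills.** It names "sterile dressing changes and VAD-related controller functions". The second term is a broad category that can take in self-tests, power sources and troubleshooting. Only the recognition of signs and symptoms clearly falls outside it.
- **That success may be claimed at any visit.** The split of Hypotheses 1a and 1b and the secondary status of decay argue against this.

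**Conclusion.** The point holds in a limited form. STUDY ENDPOINTS and DATA AND SPECIMEN MANAGEMENT contradict each other on what is primary, and the latter has two primary measures without a success rule, an explicit time point or a unit of analysis. The error-rate consequence is modest and conditional: between about 7.8% (correlation 0.8) and 9.75% (independence) in place of 5%, and only if either measure suffices and both are tested at 0.05. The unit of analysis may matter more. On the plan's means and SDs, a single-role test has about 62% power, and the stated 82% is credible only if patients and caregivers are pooled and their within-pair correlation is not large. The documents do not support a claim of error rates of 26% or 46%.

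**What to change.** 1. **STUDY ENDPOINTS.** Replace the enrolment sentence with, for example: *The primary endpoint is the total percent-correct checklist score at Time 0, compared between randomised arms at two-sided 0.05.* Add whose score is analysed. Wording that says only that skills are assessed on the patient is not enough, because caregivers also demonstrate them on the patient.
2. **Unit of analysis.** If patients and caregivers are pooled, state an analysis that accounts for the pairing, and recheck power under an assumed within-pair correlation. If one role is chosen, restate the power (about 62% at 37-38 per arm).
3. **Written examination.** Make it secondary: it has no stated test or sample size, and only caregivers are described as taking it under usual training. Alternatively, keep both measures primary with a written rule, such as 0.025 each. In that case also give the examination a test, a population and a power statement.
4. **Later visits.** State that the one- and three-month scores are secondary.

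**Cost.** The edits need no new data collection. With a single primary endpoint, examination and later-visit results can no longer be claimed as primary. With the split, checklist power at 75 per group falls from about 90% to about 83%, treating participants as independent. If one role is chosen, the lower power is a real cost that wording does not remove.

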The research settings for recruitment and enrollment of patients is Northwestern Memorial Hospital, Northwestern University, Chicago, IL. Patients will be recruited either at the medical center (while the patient is hospitalized) or during a clinic visit. The co-investigators, who provide care to patients with ventricular assist devices (VADs) will share information about the study with patients. If the patient's caregiver is not present at this time, we will contact them via phone or via mailed brochure to explain the study and then consent in person when they arrive for their VAD training.

The PI, CO-I or VAD nurse, will further explain the study to patients and caregivers, encourage them to ask questions, and obtain written informed consent. Patients and caregivers will be informed that if they decline to participate in the study, it will not prejudice current patient care, and they may discontinue participation at any time during the study with no adverse impact to their treatment or care. Verbal and written information provided to potential participants during informed consent will include the following: the purpose of the study, the nature of the questions asked during interviews, the method and frequency of skills assessment completion, the length of time required, the voluntary nature of participation in the study, the ability to not respond or participate in any parts if requested, the freedom to withdraw from the study at any time without consequences, the potential risks and benefits of study participation,

and the confidentiality of information gathered. A brochure with an overview of the study will also be provided. Patients will also be shown their study results, if desired. Patients who are enrolled in INTERMACS will also be informed that INTERMACS will securely transmit data to Northwestern, as well, which is already done for other studies. We will also incorporate language into their consent form that includes a statement about INTERMACS protected health information being transmitted securely to Northwestern. Patients who agree to participate in the study will sign an informed consent form. A copy of the signed consent form will be given to the patient, a second copy of the consent form will be placed in the patient's medical record, and the original copy will be kept and filed by the RC

NUMBER OF LOCAL PARTICIPANTS:

We expect to recruit 75 patients and 75 caregivers. One caregiver will be identified by each patient subject.

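### The target of 75 per group needs every expected implant in 15 months to enrol with a caregiver and both members of each pair to count as independent; no margin is stated

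*Combined protocol and SAP*

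**What the plan says.** **Source population.** Procedures Involved states: "Approximately 60 advanced HF patients undergo VAD implantation at NMH yearly". Study Timelines adds: "We anticipate enrollment of study subjects will take approximately 15 months".

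**Recruitment.** Procedures Involved speaks of "up to 75 participating patients and 75 caregivers". Number of Local Participants says: "We expect to recruit 75 patients and 75 caregivers", and "One caregiver will be identified by each patient subject". Inclusion and Exclusion Criteria gives the same two counts as expected recruitment. One figure therefore serves as both ceiling and expectation.

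**Conditions on entry.** Procedures Involved says "Eligible patients will be about to undergo VAD implantation at NMH, age >18, and English-speaking", and "Patients and caregivers must both agree to participate in the study to be enrolled". Inclusion and Exclusion Criteria also rules out, among others, patients whose medical condition prevents consent and those in institutions. Withdrawal of Participants allows anyone to leave at any time. No rate of ineligibility, refusal or loss is given.

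**Sample size.** Data and Specimen Management bases 82% power on 65 per group (130 in total), means of 85% and 95%, SDs of 25 and 10, and a two-sided t-test at 0.05. It then says that, because scores are unlikely to be normal, "adding 15% requires 75 in each group". The same section reports a difference of about 33 points in earlier work.

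**The concern.** The required sample equals the expected source population. Every implant patient would have to be eligible, consent, bring a consenting caregiver and be assessed. The plan's own entry rules make that unlikely, and the only inflation in the calculation is already used for the shape of the score distribution.

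The 75 per group is also a count of people. One caregiver per patient gives 75 pairs across both groups, or 150 individuals. Treating those as 150 independent observations assumes that a patient and caregiver who train together score no more alike than strangers.

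At stake is how the trial is read against its design value of 10 points. A result that shows no difference, or an inconclusive three-month comparison under Hypothesis 1b (where losses accumulate), could be judged against a power the trial may not have had. Study Endpoints also makes sufficient enrolment the primary endpoint, so the realistic number of pairs should be on record.

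**Working it through.** **1. The plan's own figures.**
- Inputs (Data and Specimen Management): difference 10, SDs 25 and 10, 65 per group, two-sided 0.05.
- Standard error = √(25²/65 + 10²/65) = √(725/65) = 3.34. The ratio of difference to standard error is 10/3.34 = 2.99.
- Power is 84.1% by Welch's t-test (noncentral t), 84.4% with pooled variance and 85.0% by the normal approximation. The stated 82% is slightly conservative. Welch with the Wilcoxon efficiency factor 3/π (effective n 65 × 3/π = 62.1) gives 82.4%; the plan does not say how it obtained its figure.
- Inflation: 65 × 1.15 = 74.75, rounded up to 75. This reproduces.

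**2. Supply against need.**
- Expected implants: 60 × 15/12 = 75.
- 75 per group = 150 individuals = 75 pairs = 100% of expected implants.
- 65 per group = 130 individuals = 65 pairs = 65/75 = 87% of expected implants.

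**3. Power by uptake.** Uptake here means pairs enrolled and assessed, as a share of 75 implants. It is an assumption, as is 1:1 allocation, which the equal group sizes imply. Individuals per group = 75 × uptake.
- The third column treats all individuals as independent.
- The fourth keeps the plan's allowance for non-normal scores by dividing n by 1.15.
- The fifth assumes that both members of a pair are in the same group with correlation ρ = 0.3 between their scores, so effective n = n/(1 + ρ).

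| Uptake | Individuals per group | Power, independent | Power, 15% allowance kept | Power, ρ = 0.3 |
|---|---|---|---|---|
| 100% | 75 | 89% | 84% | 80% |
| 87% | 65 | 84% | 79% | 73% |
| 80% | 60 | 81% | 75% | 70% |
| 70% | 52.5 | 76% | 69% | 64% |
| 50% | 37.5 | 61% | 54% | 49% |

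**4. Where power crosses 82%.**
- Welch power is 82% at 61.4 per group (81.7% at 61, 82.4% at 62). 61.4/75 = 82% uptake.
- With the allowance kept: 61.4 × 1.15 = 70.6, and 70.6/75 = 94% uptake.
- At full uptake, the correlation that brings power down to 82% is 75/61.4 − 1 = 0.22. With the allowance kept, it is 75/70.6 − 1 = 0.06.

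**5. The difference the plan expects.** From the reported values, 94.88 − 61.47 = 33.41 points, with SDs 24.48 and 6.63. At 50% uptake and ρ = 0.5, effective n = 37.5/1.5 = 25 per group, and Welch power is above 99.9%.

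**The case against.** A reader might infer that the plan's own figures fail to deliver the stated power. The documents do not support that. The 82% is attached to 65 per group, not 75. Full enrolment with independent members gives 89%, and 65 pairs give 84%. The shortfall appears only after adding an uptake or a correlation that the documents do not state. Nor do they define an ordinary level of uptake against which the design could be said to fail.

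A reader might also suppose that the 15 months must contain the three-month follow-up, leaving only about 60 implants. Procedures Involved does call the 15 months a study period, but Study Timelines gives them to enrolment and hopes to finish the analyses in two years. Fifteen months of accrual plus three of follow-up fits that, so no such scenario is used here.

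The ceiling is soft. The implant rate is approximate, and the inclusion criteria also admit people who already have a device. That wider pool conflicts with Procedures Involved, which limits eligibility to those about to be implanted, and with training that starts before implantation. It needs reconciling, but it is not a usable reserve as the study is described.

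Within-pair correlation is a separate matter from recruitment, and the unit of randomization is not stated. That stands, and so the independent column is the main result. The correlation still belongs here, because 75 pairs become 75 per group only by counting both members.

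Finally, 10 points is a deliberately cautious design value, and power for the expected 33 points is not in doubt. This stands too, and it limits the consequence.

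**Conclusion.** The concern holds as a lack of margin. The stated 75 per group is the whole expected source population, counted as individuals, with no provision for ineligibility, refusal by either member, or loss. Power for the 10-point difference is at risk rather than shown to be absent. It is below 82% if uptake is under about 82% (about 94% with the 15% allowance kept), or if within-pair correlation exceeds about 0.22 at full uptake. These thresholds rest on the plan's means and SDs, equal groups and Welch's test; the correlation figures also assume that pairs stay together in one group. The consequence is confined to the 10-point design value. A difference near 33 points would be detected at any uptake shown.

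**What to change.** Keep the enrolment plan and restate the numbers in Inclusion and Exclusion Criteria, Data and Specimen Management, and Number of Local Participants:

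- Describe about 75 as the number of implants expected in 15 months, not the number of patients expected to be recruited. It is an approximate expectation, so it should not be worded as a hard maximum either.
- Give the number of pairs expected after eligibility, joint consent and loss, with the assumed rates and, if the site has them, the screening figures behind them.
- State power for the 10-point difference at that number of pairs in a small table, over a range of within-pair correlations. Say whether the 15% allowance for non-normal scores is included, and show the three-month comparison separately.
- Reconcile the inclusion criterion that admits people already implanted with the Procedures Involved text that limits eligibility to those about to be implanted.

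The cost is text only; no procedure, visit or analysis changes. The stated power for 10 points becomes less favourable, while power for the expected 33-point difference remains above 99%.
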